In this project, we will examine individual differences in the effects of a stimulant drug, methamphetamine (MA), on mesolimbic reward function using fMRI. We will determine how individual differences in neural activity after the drug are related to its behavioral, rewarding effects. The effects of MA on mesolimbic reward function will be examined using both reward-task-related activation and resting state functional connectivity. On separate sessions, we will examine the effects of MA on behavioral reward in the same subjects, using ratings of drug liking and euphoria, as well as measures of drug seeking (drug and dose choice). Our goal is to identify neural processes that predict MA liking and 'seeking' behaviors. We have preliminary evidence that amphetamine increases striatal brain activity during a nondrug reward task, and that it facilitates frontal-striatal resting state functional connectivity. We will extend these observations to a larger sample using a more sensitive task, more refined imaging techniques, more comprehensive behavioral assessment and sufficient power to compare men and women. Healthy young adults will first undergo two fMRI scans with placebo and MA (20 mg), while performing the Monetary Incentive Delay and the Doors task. Then, they will participate in two behavioral sessions conducted in our laboratory. We will examine correlations between the neural responses and behavioral responses to MA.

**Specific Aim 1. To determine the effects of MA on regional brain activity during anticipation of reward, task-related functional connectivity and resting state connectivity.** We will examine the direct effects of a moderate dose of MA (20 mg) vs placebo on mesolimbic circuits. Imaging measures will include on regional activation during two reward tasks, task-related changes in functional connectivity, and resting state functional connectivity. These measures of assess different dimensions of brain function impacting reward processing. We hypothesize that MA will increase activation in striatal regions during anticipation of reward, and enhance both task-related and resting state functional connectivity in fronto-striatal reward circuits. We also expect that there will be inter-subject variability in these effects.

[figure not shown]

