**Imaging data analysis.** Imaging data from fMRI tasks will be preprocessed and analyzed using AFNI tools, as in Van Hedger (Van Hedger, Keedy et al. 2018). Preprocessing steps include alignment of each time series, spatial registration of the aligned time series to the anatomical scan, anatomical scan warped to standard space and warp applied to functional data, functional data spatially smoothed, and intensity normalization. Neural activation for conditions of interest from each task will be estimated using AFNI's 3dDeconvolve program, incorporating motion and heart rate/respiration as regressors. For MID, we will use a gamma response function to create activation maps for each task element: cues, motor response, and feedback. For the secondary tasks, we will use block functions and create contrast maps between the two block types. Mean activation for each subject at each scan session will be extracted from regions of interest (ROI). For MID, ROIs will be 8mm spheres created around coordinates reported in a recent meta-analysis of 50 MID fMRI studies (Oldham, Murawski et al. 2018). For Cue: caudate, putamen ventral striatum, thalamus, and anterior insula; Feedback: ventromedial prefrontal, orbitofrontal cortex, ventral striatum, amygdala, and will be a subtraction of mean activation of loss trials from win trials in each ROI (this contrast is the most common and more sensitive approach, per Oldham); Motor: all prior ROIs (to confirm lack of drug effect), primary sensorimotor cortex. ROI activation will be a subtraction of mean activation of loss trials from win trials in each ROI (this contrast is the most common and more sensitive approach, per Oldham). We will also look specifically at win vs neutral and loss vs neutral to confirm whether findings are driven by sensitivity to reward or avoiding loss. Tapping: primary motor cortex: dorsal striatum (caudate, putamen). For connectivity analyses of the MID task and of resting state, we will use the CONN toolbox (Whitfield-Gabrieli and Nieto-Castanon 2012) which employs similar preprocessing steps (alignment and spatial standardization, intensity normalization, motion estimation, white matter and CSF-based regressors) implemented through SPM12. We will use a 2mm displacement cutoff. For MID task-related connectivity, we will conduct an ROI-to-ROI analysis, using the spherical masks described previously. The toolbox allows comparison of correlation strengths (Pearson r converted to Fisher z) of the timeseries between each pairing of the ROIs. We will compare these correlations between drug and placebo sessions, as well as extract ROI-to-ROI correlation values for assessment in relation to behavioral measures. For resting state, we will calculate seed-based connectivity maps separately for MA and placebo, as per our prior study (Weafer, Van Hedger et al. 2019). Seeds will be bilateral caudate, putamen, and ventral striatum. We will conduct paired t tests within CONN to compare connectivity following MA and placebo. As our hypotheses are specific to frontal and subcortical reward circuitry, statistical inferences will be made within an anatomically-focused frontal-insular-striatal partial brain mask. The mask will include medial and lateral frontal and orbital regions, bilateral precentral gyri, anterior and middle cingulate cortex, anterior insula and ventral striatum. Drug order will be included as a covariate in all analyses.

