## **C6. Statistical Plan**

**Aim 1 is designed to determine the effects of MA on regional brain activity during anticipation of reward, as well as changes in connectivity both during the task and at resting state.** We hypothesize MA will increase activation in mesolimbic reward regions during the task and increase both task-related and resting state functional connectivity in reward circuitry. For task-related activation we will use SPSS to conduct, for each MID task component separately (cue, motor response, feedback), within-group contrasts of the MA vs PL sessions using the extracted activation from the ROIs. Based

on our preliminary data, we expect greater activation in ROIs, specifically dorsal and ventral striatal reward regions (i.e., caudate, putamen, and nucleus accumbens) following MA compared to PL for cue and feedback. Given that we did not see any effect of methamphetamine on motor cortex in our preliminary data, we do not expect to see a drug effect on motor here. Secondary, exploratory whole brain analyses will also be conducted comparing MA vs PL in each task component. To examine the effects on task-related connectivity, we will use the CONN toolbox to conduct within-group ROI-to-ROI contrasts, e.g., we will compare correlation strengths of the seed regions to one another during the MA vs. the PL scan, and expect stronger connectivity (correlation) from the MA session, specifically between striatal (i.e., caudate, putamen, and nucleus accumbens) and medial frontal (i.e., ventromedial prefrontal and orbitofrontal cortex) reward regions. To assess resting state connectivity drug effects, we will use CONN to contrast the seed-based connectivity maps from the MA vs PL sessions. CONN analyses will be evaluated at  $p < .05$ , familywise, within the fronto-insular-striatal mask. Based on our preliminary findings (Weafer, Van Hedger et al. 2019), we hypothesize greater connectivity between striatal seed regions and medial frontal reward regions (i.e., ventromedial and orbitofrontal cortex). All analyses will include drug order, age, and sex as covariates.

Power analysis for Aim 1: Our preliminary data indicate a large effect size for the effect of MA compared to placebo on resting state fronto-striatal (NAcc to OFC) functional connectivity ( $d = 0.94$ ). The proposed sample of  $N=160$  would provide over 99% power ( $\alpha = .05$ ) to detect an effect of MA on resting state functional connectivity.

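### MID task connectivity is a time-series correlation with no stated removal of task-evoked responses, so an MA effect on activation can move it, up or down, with coupling unchanged

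*Combined protocol and SAP*

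**What the plan says.** The Methods section lists task-related connectivity among the primary outcomes of the scanning sessions. Specific Aim 1 presents regional activation alongside "task-related changes in functional connectivity, and resting state functional connectivity" and describes the measures as tapping different dimensions of reward processing.

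The Imaging data analysis paragraph defines the MID measure. For the regions, "we will conduct an ROI-to-ROI analysis, using the spherical masks described previously", so the connectivity ROIs are the activation ROIs. For the statistic, "The toolbox allows comparison of correlation strengths (Pearson r converted to Fisher z) of the timeseries between each pairing of the ROIs". For its use, "We will compare these correlations between drug and placebo sessions, as well as extract ROI-to-ROI correlation values for assessment in relation to behavioral measures". C6, Aim 1 repeats the definition: "we will compare correlation strengths of the seed regions to one another during the MA vs. the PL scan".

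The preprocessing listed for the connectivity toolbox is "alignment and spatial standardization, intensity normalization, motion estimation, white matter and CSF-based regressors". Task events appear only in the activation analysis, which runs in a different package: "we will use a gamma response function to create activation maps for each task element: cues, motor response, and feedback".

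On direction, C6 states: "We hypothesize MA will increase activation in mesolimbic reward regions during the task". It then names the striatal ROIs specifically for cue and feedback. For connectivity it predicts a stronger striatal to medial frontal correlation under MA. C6, Aim 2 takes the MA-minus-PL difference for each significant ROI pair and relates it to behaviour.

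**The concern.** Two regions driven by the same events have correlated time series partly because the events drive both. If MA changes the size of the evoked response in either region, that shared part changes, and so does the correlation, even if the background coupling is identical on both days. The ROIs come from a meta-analysis of MID studies, so they are regions expected to respond to the task, and the plan expects MA to act on that response.

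An MA versus PL difference in this outcome would then not be interpretable as a change in connectivity. It could be produced by activation alone, and a true change in coupling could be masked where the activation effect works the other way. In Aim 2 the evoked part would influence both which pathways are carried forward and the scores related to drug liking. That blurs the distinction drawn in Specific Aim 2 between what resting connectivity and task activation each predict.

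**Working it through.** **The plan's own figure.** The only Aim 1 power figure is for resting connectivity: d = 0.94, N = 160, alpha .05, power over 99%. With a paired t-test the noncentrality is 0.94 × √160 = 11.89 and power exceeds 0.999, so the figure reproduces. No figure is given for MID connectivity.

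**Model.** Give each ROI unit background variance, with background coupling c that is the same on both days. Add trial-locked evoked variance vA (striatal) and vB (frontal), as a fraction of background variance. Let q be the correlation between the two evoked time courses. Then

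r = (c + q√(vA·vB)) / √((1+vA)(1+vB)).

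MA multiplies evoked amplitude by g, so it multiplies v by g². Two rules follow from the derivatives:
- If both ROIs have the same v and rise together, r = (c + qv)/(1+v), which increases only if q > c.
- If only the striatal ROI rises, r increases for a small rise only if q√vB > c√vA.

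**Inputs.** N = 160 is from the plan. The values of c, v, q and g, and the SD of the within-subject z difference (0.2 to 0.3), are assumptions; the documents give none. Rejection rates are for a two-sided paired t-test at .05 on one ROI pair, without familywise correction. Each range runs from SD 0.3 to SD 0.2.

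**Results with coupling unchanged.** c = 0.30 throughout; v = 0.10 and g = 1.3 except in the last row.

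| Case | r, PL | r, MA | Change in z | Rejection |
|---|---|---|---|---|
| Both rise, q = 1 | 0.364 | 0.401 | +0.044 | 45–79% |
| Both rise, q = 0.5 | 0.318 | 0.329 | +0.012 | 8–12% |
| Both rise, q = 0.3 | 0.300 | 0.300 | 0 | 5% |
| Both rise, q = 0 | 0.273 | 0.257 | -0.017 | 11–19% |
| Only striatal rises, q = 1 | 0.364 | 0.379 | +0.018 | 12–21% |
| Only striatal rises, no frontal response | 0.286 | 0.278 | -0.009 | 7–9% |
| Both rise, q = 1, v = 0.20, g = 1.5 | 0.417 | 0.517 | +0.129 | about 100% |

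First row in full: (0.30 + 0.10)/1.10 = 0.364. Under MA, v = 0.10 × 1.69 = 0.169 and (0.30 + 0.169)/1.169 = 0.401. The z values are 0.381 and 0.425.

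**Familywise control.** C6 evaluates the connectivity analyses at .05 familywise but does not say how ROI pairs are corrected. As an illustration, Bonferroni over the 3 × 2 = 6 striatal-frontal pairs brings the first row to 21–55%. Over all 8 × 7 / 2 = 28 pairs of the cue and feedback ROIs it is 10–35%. The last row stays at 99% or more under either.

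**Other inputs.** The table is not a bound. In these cases the evoked part is a share of total variance in each ROI and amplitude rises by 50%.
- c = 0.2, 20% share in both ROIs, same shape: r goes from 0.360 to 0.488, a z change of +0.157.
- c = 0.6, 10% share in the striatal ROI, no frontal response: r goes from 0.569 to 0.537, a z change of -0.047.
- c = 0.4, 10% share in both ROIs, opposite sign: r goes from 0.26 to 0.12, a z change of 0.121 - 0.266 = -0.146.

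**Check of the remedy.** Time series were simulated (48 trials, 600 volumes, 25 replicates) with c = 0.4, a 10% share in both ROIs and amplitude +50% in both. The unadjusted correlation shifted by a mean of +0.079 in z and was declared significant in 25 of 25 replicates. After removal of the cue, motor and feedback regressors the mean shift was -0.002, with 2 of 25 significant, compatible with 5%.

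**The case against.** **Direction.** A reader might infer that the expected rise in activation must raise the correlation and so guarantee the predicted finding. The documents do not support that. The specific activation prediction names striatal ROIs only, while the predicted pathway runs to medial frontal cortex. Caudate and putamen are cue ROIs, vmPFC and OFC are feedback ROIs, and only ventral striatum is in both lists, so similar timing cannot be assumed. The planned activation contrast is win minus loss, which can rise without any rise in total evoked variance. This objection stands: the direction is undetermined.

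**Size.** The 45–79% in the first row needs same-sign, same-shape responses rising in both ROIs, tested without familywise correction. It should not be quoted as the false-positive rate of the plan. This also stands.

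**Silence.** A reader might infer that the series are raw, or that task responses are deliberately left in. Nuisance regressors are listed, and no section says whether the toolbox step removes task effects. The supportable statement is that removal is not stated. If it is already intended, one sentence settles the point.

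**Double counting.** It is tempting to add that activation and connectivity would be counted as independent support. The plan calls them different dimensions and tests each separately; no section combines them as evidence.

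**Existing safeguards.** The CBF covariate applies only if CBF changes significantly, and it does not remove trial-locked variance. The ancillary look at whether correlations are specific to reward tasks, and the resting scan, help interpretation, but no formal comparison of task with rest is specified. Neither safeguard answers the concern.

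**Conclusion.** The concern holds in a limited form. Followed as written, the MID connectivity outcome mixes coupling with co-activation, and an MA effect on evoked responses can shift it with coupling unchanged. The shift is upward when both ROIs co-activate with similar timing, and flat or downward otherwise. In the tabulated cases the change in z is about -0.02 to +0.13. Stronger coupling, opposite-sign responses or larger evoked shares go outside that range. At N = 160 the upper part would often be declared significant, even after a correction for multiple ROI pairs; the small changes would not. All of this rests on assumed coupling, evoked variance, timing, amplitude gain and SD. What does not rest on them is that the measure, as defined, cannot tell the two explanations apart, and that Aim 2 inherits the ambiguity. The change should be made before the connectivity analysis is run.

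**What to change.** In the Imaging data analysis paragraph and in C6, state that for the MID runs the cue, motor and feedback responses, which are the events already modelled for activation, are regressed out in the toolbox's denoising step before ROI-to-ROI correlations are computed. Use these residual correlations for the MA versus PL contrast and for the Aim 2 difference scores. Report the unadjusted correlation as a sensitivity analysis.

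A generalised psychophysiological interaction may be added as a secondary analysis of task modulation. A contrast of incentive with neutral cues would have to be reconciled with the decision in the MID task description to collapse cue conditions for primary analyses. It answers a different question and gives noisier estimates, so it should not replace the main analysis.

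The cost is a little more analysis work and some loss of degrees of freedom in each run. No new data are needed.

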## **C6. Statistical Plan**

**Aim 1 is designed to determine the effects of MA on regional brain activity during anticipation of reward, as well as changes in connectivity both during the task and at resting state.** We hypothesize MA will increase activation in mesolimbic reward regions during the task and increase both task-related and resting state functional connectivity in reward circuitry. For task-related activation we will use SPSS to conduct, for each MID task component separately (cue, motor response, feedback), within-group contrasts of the MA vs PL sessions using the extracted activation from the ROIs. Based

on our preliminary data, we expect greater activation in ROIs, specifically dorsal and ventral striatal reward regions (i.e., caudate, putamen, and nucleus accumbens) following MA compared to PL for cue and feedback. Given that we did not see any effect of methamphetamine on motor cortex in our preliminary data, we do not expect to see a drug effect on motor here. Secondary, exploratory whole brain analyses will also be conducted comparing MA vs PL in each task component. To examine the effects on task-related connectivity, we will use the CONN toolbox to conduct within-group ROI-to-ROI contrasts, e.g., we will compare correlation strengths of the seed regions to one another during the MA vs. the PL scan, and expect stronger connectivity (correlation) from the MA session, specifically between striatal (i.e., caudate, putamen, and nucleus accumbens) and medial frontal (i.e., ventromedial prefrontal and orbitofrontal cortex) reward regions. To assess resting state connectivity drug effects, we will use CONN to contrast the seed-based connectivity maps from the MA vs PL sessions. CONN analyses will be evaluated at  $p < .05$ , familywise, within the fronto-insular-striatal mask. Based on our preliminary findings (Weafer, Van Hedger et al. 2019), we hypothesize greater connectivity between striatal seed regions and medial frontal reward regions (i.e., ventromedial and orbitofrontal cortex). All analyses will include drug order, age, and sex as covariates.

Power analysis for Aim 1: Our preliminary data indicate a large effect size for the effect of MA compared to placebo on resting state fronto-striatal (NAcc to OFC) functional connectivity ( $d = 0.94$ ). The proposed sample of  $N=160$  would provide over 99% power ( $\alpha = .05$ ) to detect an effect of MA on resting state functional connectivity.

Aim 2 is to determine the relationships between MA-induced changes in cortico-striatal function and positive behavioral effects of the drug (liking, and task performance). We hypothesize that MA-induced frontal-striatal activation and connectivity in reward circuits will be positively associated with behavioral measures of reward, including ratings of drug liking and attentional bias to cues. For the behavioral measures, we will first examine the degree of concordance among the different measures of MA reward (liking and attentional bias). We expect that these measures will be moderately correlated, but we also believe they measure separate components of drug reward. We will then create summary scores of drug effects (MA minus placebo) for each of the ROI's implicated in drug reward. For MID task activation, we will subtract activation during Win – Loss following placebo from activation following MA within each ROI that showed a significant drug effect. For MID task connectivity, we will subtract connectivity estimates following placebo from those following MA for each significant ROI-to-ROI connectivity pathway. For resting state connectivity, we will extract connectivity estimates from 10mm regions surrounding significant peaks for each seed, and again subtract placebo estimates from MA. These neural drug effect scores will then be analyzed in relation to each of the behavioral measures. The hypotheses are based on preliminary data (Weafer, Van Hedger et al. 2019).

a. For drug liking, we will perform linear mixed effects models for repeated measures (Hedeker and Gibbons, 2006) within SPSS25 to test the degree to which neural drug effects interact with drug and time to predict subjective measures of drug liking, measured during the behavioral phase of the study. The models will include random intercept, drug and time effects to allow for individual differences in subjective drug response and time trends, and to account for the correlation between repeated measurements. Drug order, age, and sex will be included as model covariates. The effects of interest are the two- and three-way interactions among neural drug effects, behavioral drug effects (MA vs. placebo) and time (linear and quadratic trends) on subjective liking. We hypothesize that drug liking will be correlated with NAcc-OFC connectivity.

Power analysis for Aim 2: For correlational analyses, the proposed sample size of  $N=160$  yields power over 80% to detect correlations of 0.22 and greater for a two-tailed  $\alpha=.05$  test. This corresponds to a small to medium effect size (Cohen's  $f^2 = .051$ ), and so the sample size will allow us to detect reasonable associations with good statistical power.

Ancillary analyses. The design includes several ancillary measures that will serve as important controls. During the fMRI scan, subjects will complete a simple motor task and we will examine neural responses to this task, in both reward-related and other brain areas. During the MID task, we will collect data during receipt of reward, as well as our primary measure of anticipation of reward. On the behavioral sessions, subjects will also complete cognitive tasks (Stop Task, Go No Go and Simple Reaction time), a simple motor task, and two reward-learning tasks. Cardiovascular measures will be obtained during the drug and MA sessions. These measures will allow us to investigate

individual differences in neural function (as determined by the scan) and behavioral measures, both without drug (PL session) and after drug. We will examine the specificity of any observed correlations to reward-related tasks. We will also assess MA vs PL changes identified in fMRI data against changes noted in the ASL data.

Sex differences. We will compare each of the measures in men and women (N=80, 80), and if sex differences are detected they will be included as covariates in the correlational analyses. We do not expect significant sex differences especially because women will be tested during the follicular phase of the cycle (White, Justice et al. 2002) and (Wilkinson, Khan et al. 2009). Nevertheless, we believe it is important to investigate drug responses in men and women, with sufficient statistical power.

Alsop, D. C., J. A. Detre, et al. (2015). "Recommended implementation of arterial spin-labeled perfusion MRI for clinical applications: A consensus of the ISMRM perfusion study group and the European consortium for ASL in dementia." Magn Reson Med **73**(1): 102-16.

Ballard, M. E., J. Weafer, et al. (2015). "Effects of Acute Methamphetamine on Emotional Memory Formation in Humans: Encoding vs Consolidation." PLoS ONE **10**(2): e0117062.

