Participants will be healthy young men and women (N=80, 80). They will first participate two fMRI scans, when they receive oral MA (20 mg) and PL, in random order under double blind conditions. During the scan they will complete the Monetary Incentive Delay task (MID) (Knutson, Adams et al. 2001) and the Doors task (Carlson et al. 2011) and resting state data will be obtained. The primary outcome measures during these sessions will be task-related (anticipation and receipt of reward) regional brain activation, task-related connectivity, and resting state functional connectivity. After the two scans, subjects will participate in two behavioral sessions during which they receive MA (20 mg oral) or PL in mixed order, in color-coded capsules. Subjects will complete mood and drug effects questionnaires, and cognitive tasks.

**Subjects.** Healthy men and women aged 18-35 years will be recruited from the university and surrounding community without regard to race or ethnicity, according to Protocol 13681B. Initial

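### Aim 1 states no multiplicity control for its nine or more ROI activation tests, none across resting-state seeds, and none that fits the MID ROI-to-ROI pairs, yet significance decides what enters Aim 2

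*Combined protocol and SAP*

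**What the plan says.** Section C6 (Statistical Plan, Aim 1) runs, in SPSS, "within-group contrasts of the MA vs PL sessions using the extracted activation from the ROIs", once for each MID component: cue, motor response and feedback. It names no alpha and no multiplicity method for these tests.

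The imaging data analysis paragraph defines the regions: "For Cue: caudate, putamen ventral striatum, thalamus, and anterior insula; Feedback: ventromedial prefrontal, orbitofrontal cortex, ventral striatum, amygdala". The motor phase repeats them as a control: "Motor: all prior ROIs (to confirm lack of drug effect), primary sensorimotor cortex". C6 expects greater activation in caudate, putamen and nucleus accumbens "following MA compared to PL for cue and feedback".

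The only correction in the plan is for the CONN analyses, evaluated at p < .05, "familywise, within the fronto-insular-striatal mask". On resting state, the imaging paragraph says "Seeds will be bilateral caudate, putamen, and ventral striatum". The MID connectivity analysis compares pairs of ROIs.

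Aim 2 then builds activation difference scores "within each ROI that showed a significant drug effect". It likewise builds connectivity scores for each significant ROI-to-ROI pathway and around the significant resting-state peaks.

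The status of reward receipt is not settled. The Methods section lists anticipation and receipt together among the primary outcomes. The ancillary analyses in C6 place receipt among the ancillary measures and call anticipation the primary one.

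**The concern.** The plan sets many opportunities to find a drug effect and does not say how they will be combined. The SPSS tests on ROI means are not CONN analyses, so the familywise statement does not reach them. For resting state, that statement is naturally read as control over voxels within one map, which leaves the three seeds unaddressed. For MID connectivity, a voxel mask does not define a correction over ROI pairs.

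Two things are at stake. A report that MA changes reward-region activation could rest on a single nominal result among nine. And because Aim 1 significance selects the Aim 2 scores, an undefined threshold leaves the number and identity of the Aim 2 tests undefined as well.

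**Working it through.** **The plan's own figures.** Aim 1: d = 0.94, N = 160, two-sided .05, paired t. The noncentrality is 0.94 × √160 = 11.9 against a critical value of 1.97, so power exceeds 99.9%. The stated figure of over 99% reproduces. Aim 2: r = 0.22 with N = 160 gives 80.0% power by Fisher z, and f² = 0.22²/(1 − 0.22²) = .051. Both reproduce. Neither calculation concerns the ROI activation tests.

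**Counting the tests.** Cue 5 + feedback 4 = 9. The count of five cue ROIs treats putamen and ventral striatum as separate regions; the comma is missing in the list, but C6 and the seed list separate them. Nine is a floor. The motor phase adds 8 distinct prior ROIs plus sensorimotor cortex, another 9, but these are a negative control. Any left/right split and the win-versus-neutral and loss-versus-neutral contrasts are also left out.

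**Assumptions.** Alpha of .05 two-sided per ROI test, carried over from the plan's other tests; no true effect in any ROI; equal correlation ρ between test statistics. The documents give no ρ, so a range is shown.

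**Formulae.** Independent tests: 1 − (1 − .05)^k. For k = 9, 1 − .95⁹ = 37.0%. Correlated tests, with c = 1.96:

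1 − ∫ φ(u) [Φ((c − √ρ u)/√(1−ρ)) − Φ((−c − √ρ u)/√(1−ρ))]^k du

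For predicted increases only, the lower term is dropped, which leaves .025 per test. For k = 9 and ρ = 0, 1 − .975⁹ = 20.4%.

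| Family | ρ = 0 | 0.5 | 0.7 | 0.8 | 0.9 |
|---|---|---|---|---|---|
| 9 cue and feedback ROIs, either direction | 37.0% | 26.9% | 20.2% | 16.6% | 12.4% |
| 9 ROIs, increases only | 20.4% | 13.5% | 10.1% | 8.3% | 6.2% |
| 5 cue ROIs, either direction | 22.6% | 18.3% | 14.8% | 12.7% | 10.2% |
| 4 listed striatal tests, either direction | 18.6% | 15.6% | 13.0% | 11.4% | 9.4% |

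**Seed maps.** If each of three maps is controlled at .05, 1 − .95³ = 14.3% when independent, and 10.9% at ρ = 0.7. If the two sides are seeded separately, six maps give 26.5% and 16.4%.

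**MID ROI-to-ROI pairs.** C6 names three striatal regions and two medial frontal regions, so 3 × 2 = 6 hypothesised pairs.

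**Cost of control.** Detectable d at 80% power, paired t, N = 160: 0.22 at .05; 0.27 at .05/4 = .0125; 0.29 at .05/9 = .0056. These are upper limits for Holm, whose later steps use larger thresholds.

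**The case against.** Several stronger readings are tempting, and the documents do not support them.

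- *The ROI tests will be run uncorrected, with a 20-37% error rate.* The plan is silent; it does not say that no correction will be used, and it gives no alpha for these tests. Per-map control of the seeds is likewise the natural reading and not a written rule. The 20-37% range holds only for ρ up to 0.7 and counts decreases, which would contradict the hypothesis.
- *Any significant ROI would confirm the hypothesis.* The plan states no such rule. Its prediction concerns the striatum, and a thalamus or amygdala result would not confirm it. Limiting the count to the four listed striatal tests lowers the either-direction rate to 13-19% (ρ 0.7 to 0), still above 5%.
- *The mask is unsuitable because it omits caudate and putamen.* For resting state these are seeds and need not lie in the target mask. The predicted targets are ventromedial and orbitofrontal cortex, and the mask includes medial frontal and orbital regions. The difficulty is confined to the ROI-to-ROI analysis.
- *False ROIs bias Aim 2.* Nine null tests pass 9 × .05 = 0.45 ROIs on average, and the gate gives fewer Aim 2 tests than carrying every ROI. In a null simulation at N = 160 with normal data, selecting on the mean drug effect left the later correlation test at 4.5% against a nominal 5%. What remains is that the set of Aim 2 tests is undefined.
- *d = 0.94 shows that correction costs nothing.* That value is for resting-state connectivity only. The plan gives no effect size for ROI activation.

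The prior directional hypothesis is a fair defence and narrows interpretation, but the plan does not restrict testing to the hypothesised regions.

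**Conclusion.** The concern holds as a gap in stated error control. With each test at two-sided .05 and no true effects, every reading of the ROI family above exceeds 5%: 37% down to 20% for nine tests (ρ 0 to 0.7), 12-17% at ρ 0.8-0.9, about 10-20% for predicted increases only (ρ 0.7 to 0), and 15-23% for cue alone (same range). Which figure applies depends on the alpha, the between-ROI correlation and the status of receipt, none of which the plan settles. The seed maps add a separate 11-14%, and the ROI-to-ROI pairs have no workable correction as written. This should be settled before analysis. It does not undermine the design or the plan's stated power.

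**What to change.** Amend the statistical plan as follows.

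1. Make the hypothesised striatal tests that the imaging paragraph lists the primary activation family: cue caudate, putamen and ventral striatum, and feedback ventral striatum. Apply Holm at two-sided .05.
2. Treat the remaining cue and feedback ROIs as secondary, under Holm or FDR. Keep the motor phase as a negative control.
3. Reconcile the Methods and ancillary text on whether receipt is primary. Also reconcile the feedback ROI list with C6, which expects caudate and putamen effects at feedback although neither is listed there.
4. Evaluate each resting-state seed map at familywise .05/3, or .05/6 if sides are seeded separately.
5. For MID ROI-to-ROI connectivity, correct across the six striatal-medial frontal pairs named in C6 in place of the voxel mask.
6. State that these corrected results are the gate into Aim 2.

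The cost is wording and a modest loss of sensitivity: at N = 160 the detectable d at 80% power rises from 0.22 to about 0.27 for four tests, and to at most 0.29 if all nine form one family. The plan's d = 0.94 should not be cited as evidence of power for the ROI tests.
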